6.1.5 Guidelines for continuation of treatment

See [Section 6.3](#).

6.1.6 Treatment duration

Patients will be treated with the assigned study treatment for 12 months or until radiologically documented disease progression, intolerable toxicity, start of new cancer therapy, withdrawal of consent or discontinuation due to any other reason.

Patients who are presenting clinical benefit from the treatment with combination or monotherapy and who are not experiencing unacceptable toxicity are permitted to continue treatment after the 12-month treatment period. These patients will be followed until

radiologically documented disease progression, intolerable toxicity, start of new cancer therapy, withdrawal of consent or discontinuation due to any other reason.

The definition of end of the study is reported in [Section 4.3](#).

6.2 Dose escalation guidelines (Phase 1 studies only)

Not applicable.

6.3 Dose modifications

6.3.1 Dose modification and dose delay

For patients who do not tolerate the protocol-specified dosing schedule, dose adjustments are permitted in order to allow the patient to continue the study treatment.

6.3.1.1 Dose modifications for pasireotide LAR

Patients who do not tolerate the pasireotide LAR 60 mg i.m. dose are permitted to reduce the dose to 40 mg or to 20 mg. Patients requiring a dose reduction are to return to the higher dose once the tolerability issue is resolved.

All dose changes must be recorded on the CRF.

Table 6-6 Dosing modification criteria for suspected pasireotide LAR-related toxicities

Adverse Event	Action
CTCAE grade \leq 2	No drug adjustments
CTCAE grade \geq 3 and assessed as drug related (except blood glucose changes see Section 6.1.4.5 , LFT changes see Section 6.1.5 , QTc changes see Section 6.1.4.9)	Reduce dose to 40 mg. If the AE improves to grade \leq 2 before the next administration, increase dose to 60 mg. If the dose is increased and the AE recurs at CTC grade \geq 3 the dose will be reduced back to the lower dose and shall not be increased again during the study period. If the AE does not improve to grade \leq 2 on the lower dose before the next administration, reduce the dose to 20 mg. If re-escalation of pasireotide LAR to 40 mg is not possible*, the patient will be discontinued from the study and will be followed for safety. If the AE does not improve to grade \leq 2 on the lowest dose before the next administration, the patient will discontinue the study drug and be followed for safety.
* Re-escalation of pasireotide LAR from 20 to 40 mg has to be performed within 56 days.	

The above guidance should be used for all AEs judged to be related to pasireotide LAR except for changes in blood glucose which should be followed-up as described in [Section 6.1.4.5](#), for changes in LFTs which should be managed according to [Section 6.1.5](#), and for changes in QTc which should be followed-up as described in [Section 6.1.4.9](#).

Patients whose treatment is interrupted or permanently discontinued due to an adverse event or abnormal laboratory value must be followed at least weekly until resolution or stabilization of the event, whichever comes first. Patients must be discontinued from the study if they

require a dose delay of ≥ 56 days. All patients will be followed for adverse events and serious adverse events for 56 days following the last dose of pasireotide LAR.

6.3.1.2 Dose modifications for everolimus

Dose adjustments are permitted for any adverse event suspected to be related to everolimus in those patients unable to tolerate the once-daily oral dose of 10 mg. If the administration of everolimus must be interrupted because of unacceptable toxicity, study drug dosing will be interrupted or modified according to the guidelines in [Table 6-7](#). If the toxicity is intolerable to the patient at the original 10 mg daily dose, interrupt everolimus until recovery to grade ≤ 1 ; then, reintroduce everolimus at the initial dose or lower dose level depending on toxicity type and grade ([Table 6-8](#)).

If a patient has already decreased 2 dose level (i.e., to 5 mg every other day), no further dose reduction is permitted. Patients who need an additional dose reduction will be required to discontinue the study drug.

The lower dose level introduced after tolerability issues will be maintained throughout the study.

The initial once-daily oral dose of everolimus (10 mg) can be administered at two different strengths: either as two 5 mg tablets, taken together QD, or as a single 10 mg tablet. In case a dose reduction is required due to toxicity, patients initially receiving the 10 mg strength will be provided with the 5 mg strength. Thus, they will be able to take the reduced 5 mg dose as a single 5-mg tablet.

Table 6-7 Everolimus dose level modification guidelines

Dose level	Dose and schedule
0 (starting dose)	10 mg daily
Decrease 1 dose level	5 mg daily
Decrease 2 dose levels	5 mg every other day

Table 6-8 Dosing modification criteria for suspected everolimus-related toxicity

Toxicity	Action
Non-hematological toxicity	
Grade 2 (except pneumonitis – refer to Table 6-2) (except blood glucose changes – refer to Table 6-1) (except Hepatitis B and C management – refer to Table 6-4 and Table 6-5) (except hepatic toxicity – refer to Figure 6-2)	If the toxicity is tolerable to the patient, maintain the same dose. Initiate appropriate medical therapy and monitor. If the toxicity becomes intolerable to patient, interrupt everolimus until recovery to grade ≤ 1 . Then, reintroduce everolimus at the initial dose. If the toxicity recurs at grade 2, interrupt everolimus until recovery to grade ≤ 1 . Then, reintroduce everolimus at the lower dose level.

Any hematological or non-hematological toxicity requiring interruption for ≥ 4 weeks (28 days)	Discontinue everolimus.
*Grade 3 hyperlipidemia (hypercholesterolemia and/or hypertriglyceridemia) should be managed using medical therapies	

Investigator should manage anemia as medically indicated per local standards.

Patients whose treatment is interrupted or permanently discontinued due to an adverse event or abnormal laboratory value must be followed at least weekly until resolution or stabilization of the event, whichever comes first. The patients must be discontinued from the study if they require a dose delay of ≥ 28 days. All patients will be followed for adverse events and serious adverse events for 56 days following the last dose of everolimus. All interruptions or dose modifications must be recorded on the relevant section of the CRF.

6.3.2 Treatment interruption and treatment discontinuation

Patients experiencing unacceptable toxicity (AE of grade 3 or higher, including laboratory value changes of grade 3 or higher) that the investigator considers directly attributable to the study drugs should have their dose reduced or be withdrawn from the study. [Section 6.3.1.1](#) and [Section 6.3.1.2](#) should be regarded as a guideline for the treatment of patients

experiencing adverse events which are judged to be drug-related. Any deviation from these guidelines should be discussed and approved by the sponsor.

For patients treated in the pasireotide LAR monotherapy arm or in the combination arm, in case the re-escalation from 20 to 40 mg of pasireotide LAR is not possible due to toxicity issues, the patient will be discontinued (Table 6-9). For patients treated in the combination arm, the patient will be maintained on study treatment unless the 20 mg pasireotide LAR dose cannot be re-escalated (Table 6-9). If one drug of the combination is discontinued, the combination treatment will be discontinued.

Table 6-9 Recommendations for patient discontinuation following study drug adjustment

Dose levels reached after tolerability issues	Action
Pasireotide LAR 20 mg	If re-escalation to 40 mg* is not possible, the patient will be discontinued and followed for safety
Pasireotide LAR 40 mg	Patient can be maintained on study treatment
Pasireotide LAR 20 mg and everolimus 5 mg e.o.d.	If re-escalation of pasireotide LAR to 40 mg* is not possible, the patient will be discontinued and followed for safety
Pasireotide LAR 40 mg and everolimus 5 mg e.o.d.	Patient can be maintained on study treatment
Pasireotide LAR 60 mg and everolimus 5 mg e.o.d	Patient can be maintained on study treatment
Pasireotide LAR 20 mg and everolimus 5 mg daily	If re-escalation of pasireotide LAR to 40 mg* is not possible, the patient will be discontinued and followed for safety
Pasireotide LAR 40 mg and everolimus 5 mg daily	Patient can be maintained on study treatment
Pasireotide LAR 60 mg and everolimus 5 mg daily	Patient can be maintained on study treatment
Pasireotide LAR 20 mg and everolimus 10 mg daily	If re-escalation of pasireotide LAR to 40 mg is not possible, the patient can not be maintained on study treatment
Pasireotide LAR 40 mg and everolimus 10 mg daily	Patient can be maintained on study treatment

[figure not shown]
* Re-escalation of pasireotide LAR from 20 to 40 mg has to be performed within 56 days.

All patients must have evaluations for 56 days after the last dose of study treatment. Patients lost to follow up should be recorded as such on the CRF. Patients who discontinue study drug before completing the study should be scheduled for a visit as soon as possible, at which time all of the assessments listed for the final study visit will be performed. At a minimum, all patients who discontinue study treatment, including those who refuse to return for a final visit, will be contacted for safety evaluations during the 56 days following the last dose of study drug.

Patients who discontinue study drug should be considered withdrawn from the study after the final visit assessments are performed or when it is clear that the patient will not return for these assessments.

6.3.2.1 Hepatic-related discontinuation criteria

If any of the discontinuation criteria below are met, study medication should be discontinued immediately. In addition, proper safety follow-up management should be performed as outlined in Section 6.1.5. Re-challenge of study medication is prohibited once discontinuation criteria are met.

- ALT or AST > 3 x ULN and Total Bilirubin \geq 2 x ULN and ALP < 2 x ULN;
- ALT or AST > 5 x ULN and \leq 8 x ULN persistent for more than 2 weeks;
- ALT or AST > 8 x ULN.

6.4 Concomitant medications/therapies

As underscored in [Section 1.2.2.3](#), everolimus is a substrate of CYP3A4, being metabolized by this enzyme in the liver and, to some extent, in the intestinal wall. In addition, it is a substrate and moderate inhibitor of the multidrug efflux pump P-glycoprotein (PgP). Therefore, extent of absorption and subsequent elimination of systemically absorbed everolimus may be influenced by agents that are substrates, inhibitors, or inducers of CYP3A4 and/or PgP. For example, inhibitors of PgP may decrease the efflux of everolimus from brain or tumor and therefore increase everolimus concentrations in these tissues.

[Table 6-10](#) reports a comprehensive list of relevant inducers and inhibitors of CYP3A. A strong inhibitor may cause \geq 5-fold increase in AUC or \geq 80% decrease in clearance of sensitive CYP substrates (including everolimus) whereas a moderate inhibitor may cause 2 to 5-fold increase in AUC values or 50-80% decrease in clearance of sensitive CYP substrates. Distinction is not always categorical as the interaction can vary according to certain conditions.

Table 6-10 Clinically relevant drug interaction: inducers & inhibitors of isoenzyme CYP3A4

Inducers

Strong inducers: avasimibe, carbamazepine, mitotane, phenobarbital, phenytoin, rifabutin, rifampin (rifampicin), St. John's wort (hypericum perforatum)
 
Moderate inducers: bosentan, efavirenz, etravirine, genistein, modafinil, nafcillin, ritonavir, [talviraline], thioridazine, tipranavir
 
Weak inducers: amprenavir, aprepitant, armodafinil (R-modafinil), bexarotene, clobazam, danshen, dexamethasone, Echinacea, garlic (allium sativum), ginkgo (ginkgo biloba), glycyrrhizin, methylprednisolone, nevirapine, oxcarbazepine, pioglitazone, prednisone, [pleconaril], primidone, raltegravir, rufinamide, sorafenib, telaprevir, terbinafine, topiramate, [troglitazone], vinblastine

Inhibitors

Strong inhibitors: boceprevir, clarithromycin, cobicistat, conivaptan, elvitegravir, indinavir, itraconazole, ketoconazole, lopinavir, mibefradil, nefazodone, nelfinavir, posaconazole (Krishna, et al 2009), ritonavir, saquinavir, telaprevir, telithromycin, tipranavir, troleandamycin, voriconazole.
 
Moderate inhibitors: amprenavir, aprepitant, atazanavir, casopitant, cimetidine, ciprofloxacin, cyclosporine, darunavir, diltiazem, dronedarone, erythromycin, fluconazole, fosamprenavir, grapefruit juice (citrus paraside fruit juice), imatinib, schisandra sphenanthera, tofisopam, verapamil.

A comprehensive list of cytochrome P450 isoenzymes and CYP3A4 inhibitors, inducers, and substrates can be found at http://medicine.iupui.edu/clinpharm/ddis/. This website is continually revised (Version 5.0 released on January 12, 2009) and should be checked frequently for updates.

The list of relevant substrates, inhibitors or inducers of PgP and PgP/CYP3A dual inhibitors is included in [Table 6-11](#).

[figure not shown]

Table 6-11 Clinically relevant drug interactions: substrates, inducers, and inhibitors of PgP and PgP/CYP3A dual inhibitors

PgP Substrates	PgP Inhibitors and PgP/CYP3A dual inhibitors	PgP Inducers
colchicine, digoxin, fexofenadine, indinavir, paclitaxel, talinolol, topotecan, vincristine, everolimus	amiodarone, azirhromycin, captopril, carvedilol, clarithromycin, conivaptan, diltiazem, dronedarone, elacridar, erythromycin, felodipine, fexofenadine, fluvoxamine, ginko (ginko biloba) indinavir, itraconazole, lopinavir, mibefradil, milk thistle (silybum marianum), nelfinavir, nifedipine, nitrendipine, paroxetine, quercetin, quinidine, ranolazine, rifampin, ritonavir, saquinavir, Schisandra chinensis, St John's wort (Hypericum perforatum), talinolol, telaprevir, telmisartan, ticagrerol, tipranavir, tolvaptan, valsopodar, verapamil,	rifampin, St John's wort
Reference: Internal Clinical Pharmacology Drug-drug interaction (DDI) memo, updated Oct. 29, 2012, which summarizes DDI data from three sources including the FDA's "Guidance for Industry, Drug Interaction Studies", the University of Washington's Drug Interaction Database, and Indiana University School of Medicine's Drug Interaction Table.		

In addition, *in vitro* studies showed that everolimus is a competitive inhibitor of CYP3A4 and a mixed inhibitor of CYP2D6, potentially increasing the concentrations of products eliminated by these enzymes. Thus, caution should be exercised when co-administering everolimus with CYP3A4 and CYP2D6 substrates with a narrow therapeutic index.

In contrast, pasireotide has little or no capacity to inhibit the major P450 enzymes as a direct acting (metabolism independent) reversible inhibitor, or as an irreversible metabolism dependent inhibitor. Pasireotide was found to be a weak *in vitro* inhibitor of CYP1A2, CYP2B6, CYP2C8, CYP2C19, CYP2E1 and CYP3A4/5 with IC₅₀ values ranging from 10 to >100 µM. However, based on the low therapeutic levels, no drug-drug interaction between pasireotide and comedications (as CYP450 substrates) is expected.

Pasireotide was also shown to be able to inhibit PgP (IC₅₀ = 0.85 µM) *in vitro* in the inside-out membrane vesicle system, at concentrations of up to 10 µM. However, with the low therapeutic levels (plasma C_{max,ss} <0.1) and no inhibition in cell system, as well as the permeability-limited drug concentrations at the PgP active site, a drug-drug interaction between pasireotide and PGP substrates is not expected *in vivo*.

[figure not shown]
6.4.1 Permitted concomitant therapy

The patients must be instructed not to take any additional medications (over-the-counter products) during the course of the study without prior consultation with the investigator.

The patient must be told to notify the investigational site about any new medications he/she takes after the start of the study drug. At each visit, the patient must be asked about any new medications he/she is or has taken.

All medications (other than study drug) and significant non-drug therapies (including physical therapy and blood transfusions) administered during the study must be reported in the CRF.

All medications taken ≤30 days prior to study entry should be reported on the relevant section of the CRF. The investigator or his/her designee will continue collecting information on the initiation of additional anticancer therapies up to 56 days after the last dose of study treatment.

Women of childbearing potential will be allowed to use hormonal contraception, as indicated in exclusion criterion #25.

Palliative radiotherapy or surgery may be allowed during the study but they should be discussed with Novartis Clinical Team prior to administration.

6.4.2 Permitted concomitant therapy requiring caution and/or action

The following medications should be used with caution during the study:

- Concomitant treatment with moderate inhibitors of CYP3A4 (including but not limited to amprenavir, fosamprenavir, cyclosporine, aprepitant, erythromycin, fluconazole, verapamil or diltiazem) or moderate Pgp inhibitors requires caution. If a patient requires co-administration of moderate CYP3A4 inhibitors or Pgp inhibitors, **reduce the dose of everolimus to 5 mg**. If well tolerated for two weeks, the everolimus dose can be increased to 10 mg/day. Additional dose reductions to every other day may be required to manage toxicities. If the inhibitor is discontinued, consider a washout period of at least 2-3 days (average for most commonly used moderate inhibitors) before everolimus dose is increased to the dose used prior to initiation of the moderate CYP3A4/Pgp inhibitor.
- Concomitant treatment with strong CYP3A4/Pgp inducers should be avoided. If patients require co-administration of a strong CYP3A4/Pgp inducer (like rifampicin and rifabutin), an everolimus dose increase from 10 mg daily up to 20 mg daily should be considered (based on pharmacokinetic data), using 5 mg increments. Enzyme induction usually occurs within 7-10 days; therefore, study drug dose should be increased by one increment 7 days after the start of the inducer therapy. If no safety concerns are seen with the next 7 days, the dose can be increased again one additional increment up to a maximum of twice the daily dose used prior to the initiation of the strong CYP3A4 inducer. This dose of everolimus is predicted to adjust the AUC to the range observed without inducers. However, there are no clinical data with this dose adjustment in patients receiving strong CYP3A4 inducers. If the strong inducer is discontinued, consider a washout period of at least 3-5 days (reasonable time for significant enzyme de-induction) before everolimus dose is returned to the dose used prior to initiation of the strong CYP3A4 inducer.
- Concomitant treatment with a substrate of CYP3A4 doesn't require dose modification; however, patients should be closely monitored for toxicity (Only patients receiving everolimus).

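### Section 6.4.2's fixed 5 mg everolimus dose gives no up-front reduction to a patient already held at 5 mg daily for toxicity when a moderate CYP3A4 or PgP inhibitor starts

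*Protocol*

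**What the plan says.** The inhibitor bullet of Protocol 6.4.2 covers a patient who needs a moderate CYP3A4 inhibitor or a PgP inhibitor. It has four steps:

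- The first action is to "reduce the dose of everolimus to 5 mg".
- Then: "If well tolerated for two weeks, the everolimus dose can be increased to 10 mg/day".
- Then: "Additional dose reductions to every other day may be required to manage toxicities".
- When the inhibitor stops, a washout of at least 2-3 days is to be considered "before everolimus dose is increased to the dose used prior to initiation of the moderate CYP3A4/Pgp inhibitor".

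The neighbouring bullet on strong inducers also starts from fixed doses, but it ends with a relative ceiling: "a maximum of twice the daily dose used prior to the initiation of the strong CYP3A4 inducer".

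Protocol 6.3.1.2 governs reductions for toxicity. Table 6-7 has three levels: 10 mg daily, 5 mg daily and 5 mg every other day. The section adds: "The lower dose level introduced after tolerability issues will be maintained throughout the study". For the lowest level it says: "If a patient has already decreased 2 dose level (i.e., to 5 mg every other day), no further dose reduction is permitted". It continues: "Patients who need an additional dose reduction will be required to discontinue the study drug".

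The inhibitor bullet refers neither to 6.3.1.2 nor to Table 6-7.

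**The concern.** The bullet exists because moderate inhibitors raise everolimus exposure. Its protection is a first reduction made before any harm is seen. A fixed 5 mg target delivers that only to a patient above 5 mg. Table 6-7 makes 5 mg daily the first level for patients who could not tolerate 10 mg, so for them the instruction changes nothing. The patient who tolerates full dose gets a precautionary halving. The patient with shown intolerance gets the inhibitor at an unchanged dose and waits for toxicity.

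At stake is avoidable everolimus toxicity, including the infections and non-infectious pneumonitis described in 6.1.4.1 and 6.1.4.7. In the extension phase the scheduled evaluations in Table 7-2 are every 3 months, so a reactive reduction need not coincide with one.

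**Working it through.** **Inputs**
- Dose levels (Table 6-7): 10 mg daily, 5 mg daily, 5 mg every other day (mean 5/2 = 2.5 mg/day).
- Inhibitor effect F (Section 6.4): a moderate CYP3A4 inhibitor may raise AUC 2 to 5-fold, or cut clearance by 50-80%. The two statements agree: 1/(1 - 0.50) = 2 and 1/(1 - 0.80) = 5. Section 6.4 adds that the classification is not always clear-cut. It gives no figure for drugs that inhibit PgP only.
- Assumption, not stated in the documents for everolimus: exposure is proportional to dose.

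**Formula**

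Exposure relative to before the inhibitor = (new dose / prior dose) x F.

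**First step under the current wording**
- Patient on 10 mg, moved to 5 mg: (5/10) x 2 = 1 and (5/10) x 5 = 2.5, so 1 to 2.5 times prior exposure.
- Patient held at 5 mg daily, left at 5 mg: (5/5) x 2 = 2 and (5/5) x 5 = 5, so 2 to 5 times prior exposure. As an inhibitor-free dose this is 5 x 2 = 10 to 5 x 5 = 25 mg/day. Against the 10 mg/day that was not tolerated, it is 1 to 2.5 times.
- Ratio of the two relative rises: 2/1 = 2 and 5/2.5 = 2. This is simply 10/5 and does not depend on F.

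**First step with a one-level reduction**
- Patient on 5 mg daily, moved to 5 mg every other day: (2.5/5) x 2 = 1 and (2.5/5) x 5 = 2.5. The relative rise is now the same as for the full-dose patient. The inhibitor-free equivalent is 2.5 x 2 = 5 to 2.5 x 5 = 12.5 mg/day.
- Patient on 10 mg: unchanged.

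**The other two parts, by reading the sections together**
- *Optional 10 mg/day step.* For an unreduced patient, 10 mg/day is the pre-inhibitor dose. For a toxicity-reduced patient, 6.4.2 permits the increase and 6.3.1.2 forbids it. Staying at the lower dose satisfies both, so 6.3.1.2 decides. What is missing is the pointer to it and a stated ceiling of the kind the inducer bullet has.
- *Patient on 5 mg every other day.* Section 6.3.1.2 already supplies a default: no lower level, and discontinuation if one is needed. Again 6.4.2 does not point there.

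**Reach**

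The Amendment 5 rationale counts 11 patients still on treatment across all three arms. Only those on everolimus alone or in combination can be affected. Their number is not stated.

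**The case against.** The strongest reply is that the gap is an absent automatic step, not an absence of protection. The instruction plainly addresses a patient above 5 mg. The bullet calls for caution and allows every-other-day dosing to manage toxicities. Sites ask about new medications at each visit (6.4.1), and Table 6-8 sets interruption and reduction rules once toxicity appears. All of that stands, but it is reactive; no current section gives the patient on 5 mg daily a reduction when the inhibitor starts.

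The size is also open to challenge. The ratios rest on assumed proportionality, and both patients end at the same 10 to 25 mg/day equivalent. Section 2.3 reports similar toxicity at 5 and 10 mg/day in an everolimus-octreotide study. So the clinical consequence is not demonstrated. Even so, the same absolute level means different things: at the low end one patient returns to an exposure he or she tolerated, the other to one he or she did not.

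Reach shrinks further because some listed inhibitors are excluded elsewhere: fluconazole (6.1.4.3), and grapefruit juice, other anticancer agents such as imatinib, and QT-prolonging drugs (6.4.3). Verapamil and diltiazem remain named in 6.4.2.

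A reader might infer that the protocol sends intolerant patients back to 10 mg/day. It does not. Section 6.3.1.2 is mandatory, the 10 mg step is optional and follows two tolerated weeks, 6.3.2 requires sponsor approval of departures, and Section 12 rules out authorised deviations. The sentence on stopping the inhibitor also implies that the on-inhibitor dose was meant to lie below the prior one. No exposure figure is therefore attached to that step.

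**Conclusion.** The concern holds as a minor safety wording point. The substantive defect is the missing up-front reduction for a patient held at 5 mg daily: on the assumptions above, 2 to 5 times prior exposure instead of the 1 to 2.5 times allowed to a full-dose patient. Those ratios are illustrative. They need dose proportionality and the Section 6.4 range, and they do not extend to PgP-only inhibitors. The twofold contrast needs only proportionality. The absent ceiling on the 10 mg step and the silence on the every-other-day patient are mainly missing cross-references.

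A reader might also infer that patients were harmed or that the results are in doubt. The documents show neither. They do not say that any patient was both dose-reduced and newly in need of such an inhibitor. The sample size and the completed Month 9 analysis are untouched.

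**What to change.** In the inhibitor bullet of 6.4.2:

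1. Reduce everolimus by one Table 6-7 level from the dose in use when the inhibitor starts: 10 mg to 5 mg daily, or 5 mg daily to 5 mg every other day.
2. Never exceed the pre-inhibitor dose while the inhibitor continues.
3. Cross-refer to 6.3.1.2 for patients already reduced for toxicity.
4. State that an inhibitor-driven reduction is not a toxicity reduction and is reversed once the inhibitor is stopped and washed out. The existing stop sentence then works at every level.
5. For a patient on 5 mg every other day, choose an alternative to the inhibitor, or interrupt everolimus within the existing 28-day limit after discussion with the sponsor. Automatic discontinuation could end treatment in someone with no new toxicity.

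The costs are modest but real. A patient on 5 mg daily moves temporarily to the lowest level, with no further reduction available while on the inhibitor. Table 6-9 already lets combination-arm patients remain on 5 mg every other day with pasireotide LAR 40 or 60 mg. Under Section 12.1 the wording needs a written amendment approved by the sponsor, the ethics committees and, where required, health authorities; an investigator letter should accompany it. No new visits, procedures or patients are needed.
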